# Research Proposal

---

During the treatment visits, LLLT-related cognitive enhancement will be assessed using two tasks: the psychomotor vigilance task (PVT), a test of sustained attention; and the delayed match-to-sample memory task (DMS), a test of visual working memory. These executive/cognitive processes are mediated by the frontal cortical regions that the LLLT treatments target. These tasks are the same as those approved in our previously-approved IRB protocols (2011-05-0022, 2015-09-0018).

The first test will be a pre-treatment baseline evaluation. (This will be preceded by a brief 1-minute-long introduction to both tasks; this data will not be recorded.) Then, after the first treatment with LLLT or placebo, participants will repeat the PVT and DMS tasks. Participants will again repeat the PVT and DMS tasks after the sixth (final) treatment is completed. We have previously demonstrated an improvement in performance on both the PVT and DMS tasks after LLLT treatment (Barrett and [name], 2013).

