## **7. Privacy and Confidentiality:**

The data will not be shared by other researchers for research purposes not detailed in this study. Information collected during the initial experiment screening will contain no identifying information until the participant signs the informed consent. No record will be kept of screens of persons determined not eligible for the study, or who decide not to participate. The participant will maintain control throughout the study over the content and amount of information he/she chooses to share with the experimenter, and has the right to withdraw from the study at any time without any penalty. Individuals will participate in the experiment one at a time, to prevent anyone’s choice to participate from becoming public. The performances on the reaction time tasks or the results of the questionnaires of any participant will never be revealed to another participant. Participants can skip any question on any of the questionnaires. The consent and debriefing sessions will also be conducted by a trained investigator. Privacy and confidentiality of participants will always be maintained.

Efforts will be made to ensure participant privacy within the constraints of the study design. The study visits will be scheduled in accordance to the participant’s availability as long as resources are available. These visits will be conducted only in the presence of trained research assistants. Participants will also be contacted by phone or email, depending upon their preference, to schedule appointments and for appointment reminders. Permission to leave messages will be asked at the time of screening.

One important limit or exception to maintaining confidentiality comes in regards to the investigators identifying persons who pose a risk of harm to themselves or others. Under circumstances where any participant is identified as being at imminent risk of harming themselves, confidentiality will be breached to ensure the participant’s safety. In such cases, a report of the risk will be made to the Psychiatric Crisis Services Department of the Austin Travis County Integral Care Center. If a subject indicates current suicidal ideation, we will contact the Behavioral Concerns Advice Line.

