**Statistical Plan:**

1. Primary outcome measure (PVT) will be analyzed using mixed ANOVA with 1 between-subjects factor (Treatment Group) and 1 within subjects factor (Time). Cognitively unimpaired (CU) and MCI groups will be analyzed separately. The contrast of interest will be Treatment Group by Time interaction. Alpha level of significance will be set at 0.05.
  - a. Secondary outcome measures (2Back performance, % Correct and Reaction Time) will be analyzed using mixed ANOVA with 1 between-subjects factor (Treatment Group) and 1 within subjects factor (Time). Cognitively unimpaired (CU) and MCI groups will be analyzed separately. The contrast of interest will be Treatment Group by Time interaction. Alpha level of significance will be set at 0.05.
  - b. Secondary outcome measures (2Back activation intensity within 8 *a priori* ROIs) will be analyzed using mixed ANOVA with 1 between-subjects factor (Treatment Group) and 1 within subjects factor (Time), only for participants who can perform the task to criterion (%Correct>50%). Cognitively unimpaired (CU) and MCI groups will be analyzed separately. The contrast of interest will be Treatment Group by Time interaction. Alpha level of significance will be set at 0.05 due to the exploratory nature of the analysis.
  - c. *A priori* ROIs were chosen based on prior literature. They are as follows:

ROI#	x	y	z	size (mm2)	designation
1	-33	4	56	2087	Left middle frontal gyrus
2	-5	19	44	1651	Left medial frontal/superior frontal gyrus
3	37	-63	53	683	Right superior parietal lobule
4	-49	-52	44	1333	Left inferior parietal lobule
5	-44	45	13	1139	Left middle frontal gyrus
6	33	48	15	955	Right superior frontal gyrus
7	32	5	55	553	Right middle frontal gyrus
8	47	14	3	335	Right inferior frontal gyrus

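### The primary PVT analysis is a mixed ANOVA with unstated Time levels and no missing-data rule; by default it drops early leavers, which biases the contrast materially if withdrawal depends on early response differently in the two arms

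*SAP*

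**What the plan says.** **SAP, Statistical Plan, item 1.** The method is given as: "Primary outcome measure (PVT) will be analyzed using mixed ANOVA with 1 between-subjects factor (Treatment Group) and 1 within subjects factor (Time". The test is then named: "The contrast of interest will be Treatment Group by Time interaction". The level follows: "Alpha level of significance will be set at 0.05". The analysis is split: "Cognitively unimpaired (CU) and MCI groups will be analyzed separately". The item does not say which assessments make up Time. The SAP gives no analysis population, no rule for a missing PVT, no imputation and no sensitivity analysis, and the protocol does not fill the gap.

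**Protocol, section 3, treatment visits.** The PVT schedule is: "The first test will be a pre-treatment baseline evaluation"; then "after the first treatment with LLLT or placebo, participants will repeat the PVT and DMS tasks"; and finally "Participants will again repeat the PVT and DMS tasks after the sixth (final) treatment is completed". Treatments are weekly for six weeks, so about five weeks separate the second and third tests.

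**Protocol, sections 7 and 8.** A participant "has the right to withdraw from the study at any time without any penalty". Section 8 sets a per-visit payment for those who stop early, so early leavers are foreseen. No withdrawal rate is given.

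**The concern.** Someone who leaves between sessions 1 and 6 has two of the three PVT results. The classical (split-plot) mixed ANOVA needs a value at every level of Time, so its usual implementation removes that person entirely. What is lost includes the post-session-1 score, the only evidence of how the person was responding before leaving.

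If poor early responders leave more readily in one arm than in the other, the people who remain flatter that arm. The Treatment Group by Time interaction then partly measures who stayed. This is the primary outcome, and because CU and MCI are analysed separately, each analysis rests on only part of the planned 200.

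**Working it through.** The plan gives no power, SD, correlation or withdrawal figure, so there is nothing of its own to reproduce.

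**1. Who is dropped under each reading of Time**

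| Levels of Time | Leaver with baseline and session 1 only |
|---|---|
| Baseline, session 1, session 6 | Dropped, with both results |
| Baseline, session 6 | Dropped; session 1 is unused for everyone, completers included |
| Baseline, session 1 | Kept |

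**2. Data lost.** With N = 200 (Protocol 6a) and a fraction d leaving after session 1, N × d people and 2 × N × d PVT results go. At d = 10% that is 20 people and 40 results; at 20%, 40 and 80.

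**3. Bias: assumptions (none is in the documents).** Three tests with SD 1 and correlation ρ = 0.6 between any two; higher is better; no true effect; the same withdrawal rate r in each arm. In one arm the withdrawal probability is p(z) = 1/(1 + exp(−(a − b·z))), where z is the standardised session-1 change and a is set so that the average of p is r. In the other arm withdrawal is random.

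- Variance of the session-1 change: 2(1 − 0.6) = 0.8, so its SD is 0.894.
- Covariance of the session-1 and session-6 changes: 1 − 0.6 = 0.4. Regression slope: 0.4/0.8 = 0.5.
- Mean of z among completers: m = −E[z·p(z)]/(1 − r).
- Bias after session 1 = 0.894 × m. Bias after session 6 = 0.5 × 0.894 × m = 0.447 × m.

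m was obtained by numerical integration. Rejection rates come from 10,000 simulated trials per setting, 50 per arm, complete cases, nominal 5%.

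| Slope b | r | m | Bias, session 1 (SD) | Bias, session 6 (SD) | Three-level interaction F | t-test, baseline to session 6 |
|---|---|---|---|---|---|---|
| 0.5 | 10% | 0.049 | 0.044 | 0.022 | 5.3% | 4.9% |
| 0.5 | 20% | 0.096 | 0.086 | 0.043 | 6.5% | 5.9% |
| 0.5 | 30% | 0.143 | 0.128 | 0.064 | 7.5% | 5.9% |
| 1.5 | 10% | 0.122 | 0.109 | 0.054 | 7.5% | 5.8% |
| 1.5 | 20% | 0.227 | 0.203 | 0.101 | 13.8% | 7.9% |
| 1.5 | 30% | 0.327 | 0.292 | 0.146 | 22.2% | 10.9% |

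The F test is affected more than the t-test because it also picks up the session-1 distortion, which is twice the session-6 bias. The t-test column applies if Time is baseline versus session 6.

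**4. Equal dependence.** With slope 1.5 in both arms and no true effect, session-6 bias is at most 0.004 SD and the F test rejects 4.9% to 5.2% of the time. With a true effect of 0.3 SD at both later tests, the complete-case estimates are 0.284, 0.275 and 0.266 as r goes from 10% to 30%, an attenuation of about 0.02 to 0.03 SD.

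**5. Using all observed PVT.** In each arm, regress session 6 on baseline and session 1 among completers, then evaluate at the means of everyone in that arm. This is the likelihood estimate when missingness is monotone. Its bias is within 0.003 SD in every setting of the table. Its standard error is essentially that of the complete-case estimate (for slope 1.5: 0.187 against 0.187 at 10%, and 0.215 against 0.213 at 30%).

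**The case against.** **Deletion is inferred.** The SAP never says incomplete participants are removed, and the three Time levels come from the protocol's schedule. A reader might infer that the plan prescribes listwise deletion; it does not. What stands is that it names a method whose default is complete cases and offers no alternative, and that two of the three readings of Time drop the leaver.

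**Withdrawal linked to early response is not enough for bias.** A reader might infer that any such link distorts the primary contrast, or that a complete-case ANOVA is unbiased only when withdrawal is unrelated to outcome. Step 4 shows otherwise: under the null, equal dependence in both arms does no harm. The dependence has to differ by arm.

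**The larger figures need a strong assumption.** Slope 1.5 is an odds ratio of exp(1.5) ≈ 4.5 per SD of early change, in one arm only. Nothing in the documents points to that. The control procedure includes brief real stimulation (Protocol section 3), and full payment of $200 comes only on completion (section 8), which may keep withdrawal low. This objection stands, and it is why slope 0.5 is shown. At that slope and 10% withdrawal the effect is negligible. The documents do not rule out differing dependence either; it could arise if only one treatment produced a noticeable early response.

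**A likelihood model is no cure-all.** It protects only when withdrawal depends on observed results. In step 5 this was true by construction.

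**Conclusion.** The gap is real, and a better method is available at almost no cost. It is worth correcting before analysis, but it is not evidence that the trial's result is biased.

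Under the assumptions in the working, with one-arm dependence and 10% to 30% withdrawal, bias in the baseline to session-6 contrast is about 0.02 to 0.06 SD at slope 0.5 and 0.05 to 0.15 SD at slope 1.5. The three-level interaction test then has a type I error of about 5% to 7.5% and 7.5% to 22%. With little withdrawal, or equal dependence in both arms, the complete-case test keeps close to its nominal level under the null.

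The documents fix none of the quantities that drive these figures: withdrawal rate, its dependence on response, arm sizes within CU and MCI, and within-person correlation. The range shows what could happen and is not a forecast.

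**What to change.** In SAP item 1:

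1. State Time as baseline, post-session 1 and post-session 6.
2. State whether the decision test is the overall Treatment Group by Time interaction or the baseline to session-6 contrast. If the latter, keep session 1 in the model, because it carries the information about early leavers.
3. Replace the mixed ANOVA with a linear mixed model for repeated measures fitted by REML, separately in CU and MCI: Treatment Group, categorical Time and their interaction, unstructured within-person covariance (3 × 4/2 = 6 parameters) and Kenward-Roger degrees of freedom, since stratum sizes are not stated.
4. Include every randomised participant with at least one PVT, in the assigned arm, with no listwise deletion.
5. Report withdrawals by arm and by last PVT completed, with the complete-case ANOVA as a comparison.
6. Add a simple sensitivity analysis for withdrawal that depends on unobserved outcome, such as shifting the missing session-6 values by arm over a stated range.

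The cost is SAP wording and slightly more analysis work; no new data are needed. With complete data the model addresses the same Group by Time question, although under an unstructured covariance its p-value need not equal the ANOVA's. Its main protection is limited to withdrawal that depends on observed data, hence item 6.

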**2. Purpose:**

Low-level light/laser therapy (LLLT) has been proven effective in increasing cognitive function in several photobiomodulation models (Barrett and [name], 2013; Blanco et al., 2015). LLLT shows promise in its ability to minimize or prevent the loss of cognitive function associated with cardiovascular disease in high risk patients.

Cardiovascular diseases have been determined to be associated with diminished cognitive function. An ideal solution to this issue would be to restore proper cardiovascular status through improved lifestyles. However, an alternative intervention is increasing cerebral oxygen consumption by up-regulating mitochondrial respiration using LLLT. As shown by Haley et al., 2007, atherosclerosis of the carotid artery is a strong predictor of cognitive decline. The carotid artery intima media thickness (IMT) is also recognized as a risk factor for brain damage in asymptomatic patients (Nguyen-Thanh and Benzaquen, 2009).

We believe that the beneficial effects of LLLT can be used to combat the negative cognitive effects associated with vascular disease in high-risk patients. We hypothesize that, relative to their own baseline, participants who receive LLLT will exhibit improved cognitive performance (higher task accuracy, faster reaction times) in cognitive tests and have a greater Blood Oxygen Level Dependent (BOLD) fMRI response to a working memory task post-treatment. The therapeutic response to LLLT will likely be moderated by level of carotid atherosclerosis (measured by IMT) and genes involved in lipid transport (APOE).

**3. Procedures:***Summary of general design and methodology.*

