We would classify this research study as a “non-significant risk device” study. Cognitive performance will be evaluated in working memory tasks in middle-aged and older adults across three groups: low intima media thickness (IMT) (1 STD below the mean), average IMT (mean), and high IMT (1 STD above the mean). Within each group there will be two possible interventions: the LLLT treatment or the placebo treatment. Cognitive tests will emphasize attention and executive functions, which are impaired in adults with cardiovascular risk factors (Cohen et al., 2009) and are enhanced by LLLT in young adults (Barrett and [name], 2013). Carotid atherosclerosis will be measured and documented via vascular ultrasound. BOLD-fMRI response to cognitive tasks will be measured pre- and post-treatment to determine physiological response to LLLT. 100 men and 100 post-menopausal women, aged 45 and older, will participate in this study after providing written informed consent, for 1 session of cardiovascular assessment, 1 session of cognitive testing and MRI scanning, followed by 6

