### *Sequence of events:*

#### Telephone Screening

Visit 1: Baseline cardiovascular assessment: 1 hour (Vascular Aging Lab, Bellmont Hall)

Visit 2: Baseline cognitive testing/MRI visit: 2-2.5 hours (Clinical Neuroscience Lab, Seay building; UT Imaging Research Center, Norman Hackerman Building)

*The order of Visits 1 & 2 is interchangeable. The visit that comes first will include the informed consent procedure.*

Visits 3-8: Treatment visits: 1 hour (Human Laser Lab, Seay building)

Visit 9: Post-treatment cognitive testing/MRI visit: 2-2.5 hours (Clinical Neuroscience Lab, Seay building; UT Imaging Research Center, Norman Hackerman Building)

Visit 10: One month post-treatment discontinuation cognitive testing visit: 1 hour (Clinical Neuroscience Lab, Seay building)

In an effort to reduce study burden for participants with Mild Cognitive Impairment, the visit to Bellmont Hall will be removed. Participants will come to the Seay building for all visits. They will undergo a shortened cardiovascular assessment at the Clinical Neuroscience Lab during visit 1.

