### **6b. Inclusion/exclusion.**

The primary inclusion criterion is age: subjects must be 45 years old or older. However, there are a number of exclusionary criteria. (Please see attachment: Exclusionary criteria screening checklist.docx.) Female participants will be limited to post-menopausal women. The criteria will be such that participants will be excluded that have been diagnosed with a psychotic disorder, have a history of violent behavior, are currently pregnant, or have ever been institutionalized or imprisoned. Participants with subjective complaints regarding modest decline cognitive decline from a previous level of performance will be included as long as the cognitive deficits do not interfere with their capacity for independence in everyday activities (Clinical Dementia Rating Score=0 or 0.5). Participants with CDR=0.5, who were randomly assigned to the placebo-treated group, will be given the chance to return for 6 weeks of active therapy. Thus, they will have the option to receive the potential benefits from LLLT. These visits will be offered as a courtesy and participants will not receive additional monetary compensation for them.

For the MRI, participants will be excluded if they have a history of neurological disease (e.g., large vessel stroke, seizure disorder, Parkinson's disease, clinically significant traumatic brain injury, multiple sclerosis, or brain infection/meningitis), major psychiatric illness (e.g. schizophrenia, bipolar disorder), MRI contraindications, including BMI > 40, or show evidence of large vessel stroke or clinically significant white matter disease confirmed by a licensed neuroradiologist. Participants with MCI with MRI contraindications will be enrolled in the study, but will not complete MRI scanning. Excluded participants will be encouraged to see their primary care physician for further care. Uninsured participants will be provided with low cost medical care resources in the Austin area organizations.

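### Does the 2-Back accuracy filter on the ROI analysis bias the comparison because the SAP does not say which scan it applies to?

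*SAP*

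**What the plan says.** SAP item 1b analyses 2-Back activation in eight pre-chosen ROIs by mixed ANOVA, with Treatment Group by Time as the contrast and the cognitively unimpaired (CU) and MCI groups kept apart. It does so "only for participants who can perform the task to criterion (%Correct>50"%). On error control it says: "Alpha level of significance will be set at 0.05 due to the exploratory nature of the analysis".

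The filter variable is also an outcome. Item 1a reads: "Secondary outcome measures (2Back performance, % Correct and Reaction Time) will be analyzed using mixed ANOVA".

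Protocol section 3 (Procedures) states that "BOLD-fMRI response to cognitive tasks will be measured pre- and post-treatment". In both visit schedules the first scan is at Visit 2, treatment runs over Visits 3 to 8, and the second scan belongs to Visit 9 ("Visit 9: Post-treatment cognitive testing/MRI visit: 2-2.5 hours" in the main schedule). Protocol section 2 (Purpose) expects that "participants who receive LLLT will exhibit improved cognitive performance (higher task accuracy, faster reaction times") on cognitive tests, without naming the 2-Back.

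No section of either document ties the 50% criterion to a visit.

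**The concern.** The criterion can be read in three ways: passed at Visit 2, passed at Visit 9, or passed at both. Under the last two, membership of the analysis set depends on something measured after randomisation and treatment, and the protocol hopes that treatment will improve accuracy.

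Suppose laser treatment lifts some weak performers over 50%. The treated arm would then keep people whom the placebo arm loses. If BOLD change is also related to accuracy, the two retained groups would differ in BOLD change even with no effect of treatment on activation. The direction is not known in advance. The bias would run against the treatment if BOLD change rises with accuracy, and in its favour if it falls.

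At stake are the size and power of the ROI tests. The primary PVT analysis and the 2-Back performance analysis in item 1a carry no such filter and are not affected.

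**Working it through.** The plan gives no pass rate, power or sample size for this analysis, so there is no figure of its own to reproduce. The check asks how large the bias could be under each reading.

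**Inputs from the documents.** Planned enrolment is 200 ("100 men and 100 post-menopausal women, aged 45 and older, will participate in this study"). There are two arms, two groups analysed separately, two scans and eight ROIs. An equal split gives 200/(2 × 2) = 50 per arm per group. That is an upper figure for an equal split, because "Participants with MCI with MRI contraindications will be enrolled in the study, but will not complete MRI scanning".

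**Assumed inputs.** Share failing at baseline 10% to 40%; test-retest correlation of accuracy 0.6; accuracy gain from treatment δ = 0.3 to 0.5 SD; correlation r of 0.3 to 0.5 in absolute value between BOLD change and the part of Visit 9 accuracy not explained by baseline; no true effect on BOLD.

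**Model.** Baseline accuracy A0 ~ N(0,1). Visit 9 accuracy A1 = 0.6·A0 + 0.8·e + δT, with T = 1 for laser. BOLD change = r·e + √(1−r²)·noise. The cut-off c is the failing quantile of A0.

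- Baseline only: e is independent of A0, so the bias is 0.
- Visit 9 only: E[e | A1>c] = 0.8·φ(c−δT)/(1−Φ(c−δT)).
- Both scans: with t(a) = (c−0.6a−δT)/0.8, E[e | A0>c, A1>c] = ∫φ(t)φ(a)da / ∫(1−Φ(t))φ(a)da, both over a>c. The denominator is the share retained.
- Bias = r × (laser mean − placebo mean).
- SE = √(1/(n·k_placebo) + 1/(n·k_laser)), where k is the share retained.

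**Worst corner (40% failing, c = −0.253; δ = 0.5; |r| = 0.5; n = 50).**

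| Reading | Mean e, placebo | Mean e, laser | Bias (size) | Retained, placebo / laser | SE | Test size |
|---|---|---|---|---|---|---|
| Both scans | 0.372 | 0.179 | 0.5 × 0.193 = 0.097 | 45.7% / 54.1% | 0.284 | 0.063 |
| Visit 9 only | 0.515 | 0.310 | 0.5 × 0.205 = 0.102 | 60.0% / 77.4% | 0.243 | 0.071 |
| Baseline only | 0 | 0 | 0 | 60.0% / 60.0% | – | 0.050 |

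**Range of the bias, in SD of BOLD change.**

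| Failing | Both scans | Visit 9 only | Largest test size, n = 50 |
|---|---|---|---|
| 10% | 0.016–0.040 | 0.018–0.044 | 0.054 / 0.055 |
| 40% | 0.038–0.097 | 0.039–0.102 | 0.063 / 0.071 |

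With 25 scanned per arm the largest sizes are 0.057 and 0.060. If δ = 0 or r = 0, the bias is zero under every reading.

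**Power for an assumed true effect of 0.5 SD, n = 50, bias against treatment.** At 10% failing, the both-scans filter lowers power from 64% to 57–61%. In the worst corner power falls from 42% to 29% (both scans) or from 54% to 37% (Visit 9 only).

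**A second model.** A four-variate normal simulation of accuracy and activation before and after treatment, with 5% to 30% failing, gave a bias of at most 0.055 SD (both scans) and 0.044 SD (Visit 9 only). Test size under the both-scans filter was 0.050 to 0.058 at 25 to 50 per arm. The first model gives 0.081 and 0.087 SD at 30% failing. Part of the gap is the SD unit, so its upper figures are on the generous side.

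**What a baseline-only filter keeps.** In the worst corner, the share of baseline passers who fall below criterion at Visit 9 is 1 − 45.7/60 = 23.8% on placebo and 1 − 54.1/60 = 9.8% on laser. These scans stay in. If a sub-criterion scan shifts measured activation by an assumed 0.7 SD, the contrast moves by 0.7 × (0.238 − 0.098) = 0.098 SD, about as much as the bias that was removed. At 10% failing with δ = 0.5 the shares are 6.8% and 2.0%.

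**Scale of the setting.** Eight ROIs in two groups make 16 tests at 0.05. If they were independent, the chance of at least one false positive would be 1 − 0.95^16 = 56%.

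**The case for a change.** The strongest case for a change is that the text does leave a choice open. Two analysts following item 1b could build different sets, and one of those choices conditions on a post-treatment outcome that the trial itself tests. BOLD response is part of the protocol's stated hypothesis, the failure rate could be high in MCI, and naming the scan would take a single sentence. In the calculations a baseline rule also keeps at least as many participants as a both-scans rule, and treatment cannot influence it.

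All of that stands as a description of the gap. It does not show an error. The plan commits to no post-treatment rule, and a criterion framed as being able to do the task reads most naturally as a property of the participant on entry. Nor is it established that the baseline set is the better main analysis. A performance criterion in task fMRI exists so that measured activation reflects engagement with the task, and requiring it at each scan is defensible. The baseline rule protects the randomised comparison; the both-scans rule protects the meaning of the measurement. The documents do not settle which should come first.

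The test sizes also depend on a particular null: treatment raises accuracy, yet the accuracy so gained has no effect on BOLD. If activation follows accuracy however it is gained, there is a real BOLD effect and those figures are not false-positive rates.

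**Conclusion.** The concern does not call for a change. Item 1b is silent on the scan, but this is missing detail with a harmless natural reading. Harm needs three things together: a filter that uses Visit 9, an effect of treatment on 2-Back accuracy, and a link between accuracy and BOLD change. The documents give evidence for none of them.

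If all three held, the bias would be about 0.02 to 0.04 SD at 10% failing and about 0.10 SD at most, reached only with 40% failing, a 0.5 SD accuracy gain and a correlation of 0.5 together. Test size at 50 scanned per arm would be at most 0.055 and 0.071 respectively. These figures rest wholly on assumed failure rates, correlations and accuracy gains, and on an equal split of the planned 200.

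That is minor beside 16 unadjusted tests in an analysis the SAP itself labels exploratory. Fixing the baseline reading would exchange one possible distortion for another of similar worst-case size. An analyst can choose either set and report how many fail by arm and visit. No conclusion on the primary outcome or on item 1a depends on it.

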Neuroimaging will be conducted at the UT Imaging Research Center in the Norman Hackerman Building. Participants will be asked to change into medical scrubs and to store their personal items in a locker. Upon entering the magnet room, participants will be given earplugs to wear (specially chosen to limit the sound intensity produced by the MRI scanner). They will be instructed to lie supine on a table. Participants will place their head inside a standard head coil. In order to acquire MR images, it is necessary that the subject's head does not move appreciably; they will therefore be outfitted with pads and wraps. We will adjust the head stabilizers until both stability and participant comfort are attained. At this point, any cables connecting the coil array to the scanner will be inspected and adjusted to guarantee the absence of any loops or direct contact with the subject. The table will then be slid into the scanner so that the participant's head and upper body are inside the scanner tube.

Once in the scanner, participants will always be given a "squeeze ball" as a top-priority communication device. They will be instructed that squeezing the ball indicates that they wish to stop the scan and/or need immediate assistance. This sounds an alarm in the control room where the researchers sit while running the MRI scanner. The scanner will be stopped if the alarm sounds during a scan. Standard communication and instruction is performed via a built-in intercom system. Participants will also be given a response pad for use during the cognitive task.

A typical scan session will take approximately 40 minutes. We will begin by taking a few anatomical MR images of the participant's brain (6-10 minutes). We will then collect a series of functional MR images (12 minutes) while the subject views visual displays and performs the cognitive and control tasks. Acquisition of magnetic resonance spectroscopy (MRS) and resting state functional MR data will take an additional 20 minutes. Participants will not be required to do anything during those acquisitions. Participants will be encouraged to terminate the session if they become uncomfortable in any way.

*Treatment visits: Low-level light therapy.*

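### The 2-Back cut of more than 50% correct does not show, under common response formats, that a participant is doing the task, so the activation analysis can admit non-performers

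*SAP*

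**What the plan says.** SAP item 1b covers "Secondary outcome measures (2Back activation intensity within 8 *a priori* ROIs"). It uses a mixed ANOVA with the group-by-time interaction as the contrast, run separately in the cognitively unimpaired and MCI cohorts. Inclusion is "only for participants who can perform the task to criterion (%Correct>50" per cent). On error control the item says "Alpha level of significance will be set at 0.05 due to the exploratory nature of the analysis".

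Item 1a uses the same score as an outcome: "Secondary outcome measures (2Back performance, % Correct and Reaction Time").

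The protocol adds little about the task. Section 2 hypothesises that treated participants will "have a greater Blood Oxygen Level Dependent (BOLD) fMRI response to a working memory task post-treatment". In section 3, under the cognitive testing/MRI visit, the statements that bear on the task are "Participants will also be given a response pad for use during the cognitive task" and "We will then collect a series of functional MR images (12 minutes"), and those minutes are shared between cognitive and control tasks. The section 3 summary says "BOLD-fMRI response to cognitive tasks will be measured pre- and post-treatment to determine physiological response to LLLT".

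Neither document states the number of response options, the target share, the number of 2-Back trials, whether % Correct runs over all trials or targets only, how omissions count, or which scan must meet the criterion.

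**The concern.** The criterion is the only evidence item 1b requires that a participant was engaged in working memory during the scan. In a two-choice task, 50% is what guessing gives on average. Raw % Correct can also be well above 50% for someone who gives one answer throughout, if that answer is the commoner one or the only one scored. A cut at this level separates performers from non-performers poorly.

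Two things are at stake. Scans from people not doing the task would pull the activation contrast towards zero. Also, 2-Back % Correct is an item 1a outcome that treatment is hoped to improve. If the post-treatment scan must also pass, inclusion depends on something treatment may change, and the two arms may no longer be comparable.

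**Working it through.** **Inputs.** The only figure from the documents is the strict cut of more than 50% (SAP item 1b). It comes with no derivation, so there is nothing to reproduce. Trial counts N = 40, 100 and 150 and target shares q = 20-40% are assumptions, chosen to show a range.

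**1. Coin-flip guesser, two choices, all trials scored.** Expected score is 50% for any q. With X ~ Binomial(N, 0.5) and N even, P(pass) = P(X > N/2) = ½[1 − C(N, N/2)/2^N].

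| N | P(pass one scan) | P(pass both scans) | Smallest score with guess pass rate ≤ 5% |
|---|---|---|---|
| 40 | 0.437 | 0.19 | 26/40 = 65% |
| 100 | 0.460 | 0.21 | 59/100 = 59% |
| 150 | 0.467 | 0.22 | 86/150 = 57% |

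The third column is the square of the second and assumes independent sessions.

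**2. Constant answer, all trials scored.** Always non-match scores 1 − q: 80%, 75%, 67% and 60% at q = 20%, 25%, 33% and 40%. It passes every time. The same holds in a press-on-target format if a withheld press on a non-target counts as correct. Always match scores q, here 20-40%, and fails. At q = 50% either constant answer scores exactly 50% and fails the strict cut.

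**3. Targets only scored.** Always match scores 100% and passes; always non-match scores 0% and fails. With 20 targets, random pressing at rates of 20-33% passes with probability 0.0006 to 0.035. Pressing at 50% passes with probability 0.41.

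**4. Omissions scored as errors.** If a guesser misses 20% of trials, the chance of a correct trial is 0.5 × 0.8 = 0.4. P(X > N/2) is then 0.074, 0.017 and 0.005 at N = 40, 100 and 150.

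**5. Dilution.** If a share f of those included carries no treatment effect on activation, the mean effect is multiplied by (1 − f). The documents give no f. For illustration, f = 10% leaves 0.90 of the effect and f = 20% leaves 0.80.

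**6. A cut that a constant answer cannot pass.** Balanced accuracy is (hit rate + correct-rejection rate)/2. Always match gives (1 + 0)/2 and always non-match gives (0 + 1)/2, so both score 50%. For a guesser, hits ~ Binomial(T, 0.5) and correct rejections ~ Binomial(F, 0.5), independently, where T and F are the target and non-target counts. Enumerating all pairs at 20% targets gives the smallest cut with pass probability at most 5%:

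| N (T, F) | Balanced-accuracy cut | Guess pass rate at that cut | Guess pass rate if the step 1 cut is used instead |
|---|---|---|---|
| 40 (8, 32) | 67% | 4.9% | 6.7% |
| 100 (20, 80) | 61% | 5.0% | 7.4% |
| 150 (30, 120) | 59% | 4.7% | 7.7% |

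The last column shows why a binomial bound on the total trial count is not enough: balanced accuracy is more variable when targets are few.

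**The case against.** The strongest reply is that the documents do not fix the chance level. A response pad need not mean two choices, and % Correct may not run over all trials. Under some ordinary scorings the cut works well: with omissions as errors and 20% missed, few guessers pass (step 4), and with targets-only scoring someone who never responds scores zero. This stands. A reader might infer that 50% is at or below chance for every match/non-match task, or that any constant answer passes. Neither follows: only the favourable constant answer passes, and an exact 50% fails.

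It can also be said that participants may practise the scanner tasks beforehand (protocol section 3), that enrolment is limited to CDR 0 or 0.5 with preserved independence (protocol section 6b), and that the analysis is secondary and labelled exploratory. These points limit the likely number of non-performers and the consequence. A reader might infer that the problem is worst in the MCI cohort. That is plausible, but the documents give no task-failure rate for either cohort.

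The exploratory label does not answer the point. The SAP attaches it to the alpha level, and it does not make the inclusion rule a valid test of task performance.

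**Conclusion.** The point holds conditionally. As written, the criterion cannot be shown to exceed chance. Under a two-choice format with all trials scored, it passes 44-47% of coin-flip guessers at 40 to 150 trials, and it passes constant non-match responding whenever targets are under half of trials. Under targets-only scoring it passes constant match responding. Those figures rest on assumed formats, trial counts and target shares.

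The rule can therefore admit non-performers. A reader might go further and conclude that the analysis does admit them, or that its effect is diluted by a known amount. The documents support neither, because they report no 2-Back scores and no share of disengaged participants. The dilution factor also assumes that such participants carry no treatment effect at all.

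The consequence is confined to item 1b. The primary PVT analysis and the item 1a performance analysis do not use this criterion. This is a cheap improvement to an exploratory secondary analysis and does not threaten the trial's main conclusion.

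**What to change.** In SAP item 1b:

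- Define % Correct: which trials are scored, how omissions count, the response format, and the numbers of target and non-target trials. State the chance level that follows.
- Replace the 50% cut with an above-chance rule on a measure that a constant response cannot pass, such as balanced accuracy or d-prime. Take the cut from the exact chance distribution for the actual target and non-target counts. At 20% targets, the balanced-accuracy cut is about 67%, 61% and 59% for 40, 100 and 150 trials.
- Apply the rule to the baseline scan only, so that treatment cannot affect who is included.
- Report the analysis in all scanned participants as a sensitivity analysis, with the number excluded by arm and cohort.

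The cost is SAP wording, some re-scoring and a somewhat smaller imaging subset. Re-scoring assumes that trial-level 2-Back responses were recorded. Protocol section 5 describes trial-level variables for the PVT and DMS but not for the 2-Back, so this should be confirmed first.
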